**I. Procedures Schedule**

**II. Informed Consent Form Template**

**III. Other (add as many appendices as necessary)**

## PRÉCIS

### Study Title

Implementation of the Care Ecosystem training model for individuals with dementia in a high-risk, integrated care management program.

### Objectives

Our primary objective is to test the feasibility of collecting emergency department visit data among the PLWD cared for by the primary care practices.

Our secondary objective is to determine the short-term impacts of an adapted Care Ecosystem curriculum and workflow on care management processes, healthcare utilization, behavioral symptoms of dementia, caregiver burden, and caregiver depression.

### Design and Outcomes

We propose a pragmatic randomized quality improvement pilot trial to assess the feasibility and effectiveness of an adapted Care Ecosystem dementia care training for pre-existing nurse care managers who provide care management to high risk patients. We will work with iCMP medical and operational leaders to engage 30 targeted nurse care managers who serve PCP practices with the highest proportions of minority / low SES patients. 15 iCMP nurse care managers will be randomly assigned to receive early Care Ecosystem training and the remaining 15 will be assigned to received delayed Care Ecosystem training. Persons with dementia (PWDs) and their caregivers will not be informed whether their nurse care manager has received Care Ecosystem training, and will therefore be masked to the assignment of their care manager.

Data and outcomes to be included in the QI study will include:

- (1) iCMP key process measures to be extracted from Epic documentation system (patient status, number of contacts between nurse manager and patient and/or caregiver, community resource requests)
- (2) Medicare claims data (health care utilization and costs)
- (3) Epic clinical data (caregiver strain and depression, behavioral symptoms of dementia, medication reconciliation, documented serious illness conversations/advance care planning)
- (4) Semi-structured interviews of nurse care managers
- (5) Surveys of caregivers to augment data captured in Epic clinical data and allow for evaluation of short-term impacts of enhanced training (caregiver strain and burden, caregiver depression symptoms, patient behavioral symptoms of dementia and patient quality of life for PWD).

### Interventions and Duration

The adapted Care Ecosystem intervention will include three distinct phases:

- (1) Developing an adaptation of Care Ecosystem training and workflows through feedback from a workgroup consisting of recently retired highly experienced iCMP nurse care managers, an iCMP medical director, a dementia expert, pharmacist, and an active caregiver.
- (2) Training of iCMP nurse care managers in the adapted version of Care Ecosystem (e-learning modules and workflows, 1-day in-person training).
- (3) Implementing the adapted Care Ecosystem intervention with trained nurse care managers.
- (4) Booster sessions and process audits to augment intervention fidelity

We will compare the outcomes detailed above between the early training nurse cohort and the delayed training nurse cohort.

We plan to spend the first 3 months of the project collecting feedback and adapting the training. Nurse care managers will be trained at the end of month three. Outcome measures will be collected at the end of month nine. The delayed training cohort will receive training in month ten.

### **Sample Size and Population**

Preliminary estimates based on 2018 data suggest that on average FTE nurse care managers in our health system have 10 Medicare beneficiaries diagnosed with dementia on their panels. For this pragmatic quality improvement trial, we plan to engage 30 active iCMP nurse care managers serving approximately 300 PWD and their caregivers. These 30 nurses represent roughly half of all existing nurse care managers. Because of the pilot nature of this QI intervention and budget limitations we do not plan to engage all nurses, rather we will seek to engage nurse care managers serving the largest proportions of minority / low SES patients. This pilot will provide information that will guide future large-scale implementations of the adapted Care Ecosystem training inside and outside of Partners Healthcare.

While all patients receiving care from these nurse care managers may be impacted, we will measure process and outcomes only among the estimated 300 PWD and caregivers who have an indication of dementia within Medicare claims data and are actively receiving care management services from the nurse care manager at the time of early training (end of month 3).

## **1 STUDY OBJECTIVES**

### **1.1 Primary Objective**

The primary objective of this study is to establish the feasibility of collecting emergency department visit data among the PLWD cared for by the primary care practices.

### **1.2 Secondary Objectives**

The secondary objective of this study is to measure short term impacts of the adapted Care Ecosystem training on PWD and their caregivers.

## **2 BACKGROUND AND RATIONALE**

### **2.1 Background on Condition, Disease, or Other Primary Study Focus**

The prevalence of Alzheimer's Disease (AD) and related dementias, currently affecting 5.8 million Americans, is expected to increase to 14 million by the year 2050, with annual costs escalating from \$290 billion to \$1.1 trillion. Nearly half the individuals with dementia in the US are not diagnosed, and amongst those who are, 50% are not informed of their diagnosis, while most are identified during the moderate stage of the illness. Dementia adversely impacts caregivers, who provide 16 million hours of unpaid care per year for individuals with AD and related dementias, and suffer greatly from stress, depression, anxiety, and health problems, which often leads to poor outcomes for their loved ones with dementia. Furthermore, behavioral symptoms of dementia, including agitation and depression, are nearly universal over the course of the illness and substantially contribute to elevated risks for morbidity, mortality, utilization of costly acute health care services, caregiver stress and long- term care placement. Primary care physicians report a lack of time, training and resources to systematically screen for, diagnose, and treat dementia, as well as to provide adequate psychosocial support to unpaid caregivers. This may lead to inadequate advance care planning and contribute to avoidable ED visits, hospital admissions and medical interventions as the disease progresses. Prior studies have demonstrated that enrollment in a collaborative care program for dementia is associated with improved functioning and quality of life, reduction in behavioral symptoms of dementia and a decrease in caregiver burden with a net cost savings as high as \$2800 annually per patient. Many of these programs are, however, resource intensive, requiring the creation of new clinical teams embedded in primary care settings. Recently, a telephone-based collaborative dementia care intervention (Care Ecosystem), that provides personalized support and standardized education through care plan protocols delivered by trained health care navigators, has demonstrated lower rates of ED utilization and reduced caregiver depression and burden.

The Care Ecosystem (CareEco) model uses a telephone-based intervention to support persons with dementia (PWDs) and their caregivers, screening for common dementia-related problems and providing modular standardized support protocols and caregiver education. Specially trained health care navigators systematically identify needs and address health status, advance care planning, medication management and management of challenging behaviors. Health care navigators receive backup support from a nurse,

social worker, dementia specialist, and pharmacist, and maintain close communication with the primary care provider of the PWD. CareEco was found to reduce ED utilization, improve PWD quality of life and improve caregiver outcomes. While the healthcare navigators used in CareEco offer clear value, this model, if adopted in a system with established, robust care management teams and no preexisting health care navigators, could actually increase cost by adding personnel in the setting of limited space and resources. We hypothesize that adapting the CareEco model to augment the dementia care provided by a pre-existing care management team could improve care manager self-efficacy in supporting PWDs, improve outcomes for PWDs and their caregivers, and optimize sustainability by enhancing dementia care competency of existing clinicians. In the proposed pragmatic clinical trial pilot, we will develop and test an adapted form of the CareEco intervention with experienced Integrated Care Management Program (iCMP) nurse care managers engaged in the care of high-risk, high-cost patients in a large health system. The strategic priorities of our health system are aligned with this work, both as a tool to provide higher-quality care to a high-risk population and as an opportunity to reduce ED visits and avoidable costs.

The integrated care management program (iCMP) at Partners HealthCare is a nurse-led longitudinal care management program embedded in Primary Care practices across the Partners network that provides care management support to the most medically complex and seriously ill patients. iCMP care managers assess each patient to clarify problems, identify barriers to accessing clinical care and community-based services, including the social determinants of health, and create a patient-centric care plan. The iCMP program serves all payor populations and has cared for over 38,000 patients since 2012.

Approximately 14,000 patients are presently enrolled in iCMP, 64% of whom are Medicare beneficiaries. An independent evaluation of Medicare patients in iCMP, relying on 18 months of claims data post-iCMP assessment, found an average savings in total medical expense (TME) of \$101 per member per month. iCMP teams care for many patients with dementia, but are not specifically trained in the care of persons with dementia (PWD) and their caregivers. iCMP care managers have described lower levels of self-efficacy in the care of PWD. An analysis of cognitive disorders within the Partners system identified a conservative estimate of dementia prevalence of 8.8% among iCMP Medicare patients based on ICD-10 diagnosis codes for dementia, as compared to a roughly 5.1% prevalence of dementia among all Medicare patients. Thus, the iCMP program provides an opportunity to train nurse care managers in an adapted CareEco model for dementia patients.

## 2.2 Study Rationale

The Care Ecosystem model is a telephone-based care program that provides standardized, proactive, personalized, and scalable support and education for caregivers, medication guidance, and promotion of proactive decision-making. It has demonstrated an improvement in patient quality of life and reduced unnecessary healthcare expenditures. The CareEco intervention makes readily available an implementation protocol toolkit that includes care protocols, educational materials, and online training.

In the original study, a Care Team Navigator (CTN) and the PWD-caregiver dyad were at

the center of the intervention. The CTN first conducted a structured needs assessment scripted for CTNs that covered immediate needs, responded to immediate concerns and then reached out proactively to work with the dyad on caregiver support and education; medications; planning ahead for medical, financial, and legal decisions; and managing behaviors. The needs assessment was either completed in the first call, or in several calls over the first few months. While the content of the care included structured components and evidence-based protocols, the focus of the care was always tailored to the needs of each dyad. Issues that exceeded the CTN's scope were triaged to a specialist team that included a dementia specialist, pharmacist, nurse and social worker. CTNs telephoned dyads at approximately monthly intervals for 12 months with phone frequency adjusted according to each dyad's needs and preferences. All follow-up calls included screening for significant incidents (that may or may not result in ED/hospital visits), as well as changes in medication, behavior, and function. They also followed-up on progress and/or adjustments to goals discussed previously as well as the caregiver's wellbeing. Participants who declined regular contact were offered a "light" version of the intervention and were sent personalized educational materials via mail or email. This study was conducted in both urban (San Francisco Bay Area) and rural (Nebraska) settings.

As noted in the background, PWD receiving CareEco had improved quality of life and reduced emergency department visits. Caregivers experienced decreased depression and caregiver burden within the first 6 months. The evidence from the CareEco trial, therefore, supports a pragmatic trial as a next step. Since the conclusion of the CareEco study, an academic health system in Colorado, an integrated health system in Minnesota, and an academic integrated health system in New Orleans have all adopted CareEco as a care delivery model. They used the Open-access CareEco tools (toolkit, educational materials, data dictionary) to develop projects at each of their sites, demonstrating that it is feasible to adapt and implement CareEco in diverse settings. While CareEco has been adopted by 3 other health systems, none of these systems are formally evaluating its implementation in an embedded trial. In the original clinical trial, the intervention posed minimal risk, with no indication of adverse events or unintended consequences.

Under value-based contracts, care management programs, and in particular care management embedded within primary care practices, have become a common strategy to address inappropriate utilization among complex patients. We propose to build on this model and test an adaptation of Care Eco that involves uptraining existing primary care embedded nurse care managers rather than adding a new care navigator to address the needs of PWD and their caregivers. This adaption both improves the fit with our health system and would be applicable to many other accountable care organizations with existing high-risk care management programs. We anticipate that this adaptation will enhance scalability by using pre-existing staffing infrastructure, improve efficiency by weaving dementia care into an established care delivery model, and optimize sustainability by matching evidence-based workflow protocols with engaged clinicians (iCMP nurse care managers).

### **3 STUDY DESIGN**

A description of the trial design should include:

- This is a pragmatic embedded randomized pilot trial of an adapted Care Ecosystem training model for nurse care managers. The primary outcomes will assess the feasibility of collecting emergency department visit data among the PLWD cared for by the primary care practices. Secondary outcomes will provide early indicators of program effectiveness.
- The setting for the intervention is the Partners HealthCare primary care-based integrated care management program (iCMP). The program is available in all 182 Partners primary care practices serving adult patients. Partners HealthCare is a non-profit integrated delivery system created by the merger of the Massachusetts General Hospital (MGH) and Brigham and Women's Hospital (BWH). Partners primary practices serve patients residing in New Hampshire, and central and eastern Massachusetts. iCMP has been a network-wide population health program since 2012, and has strong evidence of effectiveness . iCMP employs registered nurses, social workers and community health workers who manage care for approximately 14,000 adult patients.
- The original Care Ecosystem model that our intervention will be based on is a telephone-based intervention to support PWDs and their caregiver, screening for common dementia-related problems and providing modular standardized support protocols and caregiver education. Specially trained health care navigators identify needs and address health status, advance care planning, medication management and management of challenging behaviors. The intervention will occur via 1) development of an adaptation of the CareEco training through feedback from a task group; 2) training of iCMP nurse care managers in the adapted CareEco model; 3) implementing the adapted CareEco intervention with existing nurse care managers.
- We will train iCMP nurse care managers, already assigned to work with PWD and their caregivers, in the Care Ecosystem model. In collaboration with iCMP leadership we will identify 30 nurse care managers serving primary care practices with the highest proportions of minority / low SES patients. These nurse care managers will be randomly assigned to receive either early or delayed Care Ecosystem training.
- We anticipate that nurses who receive training will change the way they provide care to all their patients with dementia. However, measurement of patient-level process and outcome measures will be among patients who have an indication of dementia within their Medicare claims data and who are actively engaged with care management as of the date care managers in the early training cohort are trained. Preliminary estimates based on 2018 data suggest that on average nurse care managers have 10 Medicare beneficiaries diagnosed with dementia on their panels, yielding approximately 300 PWDs and their caregivers (150 patients in each arm).
- We will spend the first 3 months of the project collecting feedback and adapting the training. The nurse care managers who are assigned to receive

early training will be trained at the end of month three, while those assigned to receive delayed training will be trained at the end of month 9.

- Adapted Care Ecosystem training for the nurse care managers will occur via video-based learning as well as a 1-day in-person training held at the Assembly Row headquarters of Partners HealthCare.
- Study subjects include patients receiving care from 30 nurse care managers serving primary care practices with the highest proportions of minority / low SES patients. Nurse care managers will be randomly assigned to early vs. late training. Preliminary estimates based on 2018 data suggest that on average nurse care managers have 10 Medicare beneficiaries diagnosed with dementia on their panels, yielding approximately 300 PWDs and their caregivers overall; 150 receiving care management from nurses who receive early training, and 150 receiving care from nurses who receive delayed training. PWD and their caregivers will be blinded as to the timing of Adapted Care Ecosystem training of their iCMP care manager.
- All measurement and analysis will be performed by the study team using data housed within an existing Partners IRB approved Population Health Data Repository, or new quality improvement data collected by members of the study team.

#### **4 SELECTION AND ENROLLMENT OF PARTICIPANTS**

The study population will consist of all persons with dementia who receive care from 30 selected iCMP nurse care managers. Only nurses who have been completely trained and onboarded into iCMP and with existing patient panels (e.g. 6 or more months of experience) will be asked to participate in the Care Ecosystem Training during this pilot period. The training will be provided as part of on-going QA activities within the program, and similar to other training programs participation by individual nurse care managers will be optional. The study team will work with clinical and operational leaders of the program to reach out to the 30 identified nurse care managers and schedule them for early or delayed training. As the enhanced Care Ecosystem training will provide necessary skills for care managers, it will be implemented as a quality improvement trial.

All PWD who are actively receiving care management services from a selected nurse care manager at the time of early training (end of month 3) will be included in the study. PWD will be identified based on the presence of one or more diagnosis code consistent with dementia during the year ending July 31, 2020. Preliminary estimates based on 2018 claims data suggest that a total of 300 PWD will be included in the study. Caregivers of PWD will be identified using Epic documentation. This study will primarily leverage existing patient data collected within the Epic clinical record and medical claims. These data will be augmented with surveys of PWD caregivers to allow for preliminary evaluations of effectiveness. Both existing data and surveys pose minimal risks to patients. Surveys will include standard language informing caregivers that their decision to participate in the survey will not impact their care or Medicare

benefits, that their participation is voluntary and that the information gathered will only be used to improve care quality for PWD and their caregivers.

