#### 4.3 Study Enrollment Procedures

- The investigative team has presented this study to iCMP leadership prior to funding. The study team will attend an iCMP operations team meeting to discuss the Care Ecosystem training and expectations for participation in training. Calendar year 2019 data will be used to determine the percentage of minority / lowest SES patients within the practices each care manager serves. The study team will collaborate with iCMP leadership to identify 30 nurses, prioritizing nurses who serve the most disadvantaged practices. These nurses will be randomly assigned to either early or delayed training. An e-mail co-signed by the investigator leading the training and iCMP leadership will be sent to the selected nurses informing them of their training date. Limitations in funding do not allow for training of all 87 nurse care managers within this pilot.
- Nurses will be asked to complete an assessment of baseline dementia care knowledge and skills prior to their training.
- Patients who actively receive care management from the 30 identified nurses and who have a diagnosis of dementia within Medicare claims data will be identified as PWD for this study. We will leverage existing data within EPIC to identify caregivers for these PWD.
- Preliminary examination of the structured fields within Epic that are used to house information on caregivers suggests that we will likely need to develop alternative methods, including review of notes, for identifying caregivers.

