- (2) **Training iCMP nurse care managers in the adapted version of CareEco.** Prior to the 1-day in-person training, the care managers will engage in approximately 60 minutes of e-learning of the abbreviated video training. The virtual training through video technology (secure Zoom platform) will occur all in one day and will address communication skills, the use of the CareEco protocols, documentation expectations and workflow concerns. For their involvement, iCMP care managers will receive a stipend and CEU credits. On a weekly basis, the intervention team will offer an hourly check-in to address any questions that arise. The iCMP nurse care managers will also have access to a dementia care expert, in addition to their pre-existing social work and pharmacy team. The intervention team will monitor for intervention fidelity and work with iCMP nurse care managers if deviation from the adapted assessment and protocols are observed. Nurses in the early training cohort will receive their training in month three or month four, while nurses in the delayed training cohort will receive their training at the beginning of month ten.
- (3) **Implementing the adapted CareEco intervention with trained nurse care managers.** The adapted CareEco model will be delivered by the iCMP nurse managers within Partners HealthCare to patients on their panels as clinically appropriate. All care to PWD and their caregivers will be delivered over the phone. The care managers will always address immediate needs first, then screen for common problems and provide personalized support and standardized education using the adapted CareEco Care Plan Protocols; Medications, Safety, Referrals and Caregiver Education, Caregiver Well-being, Behavior Management, and Advance Care Planning. Call frequency will be about monthly but personalized to each dyad's needs and preferences. The study team will offer booster sessions and coaching over the course of the study to iCMP nurse managers who either ask for assistance or who, through chart audits, do not appear to be integrating the training into the care of their PWD. Implementation will occur following completion of training for the nurse care managers randomized to the early training cohort.

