- Caregiver Survey: All caregivers of PWD (among the eligible cohort) will be asked to participate in a survey at months three (prior to the launch of the CareEco intervention) and nine. A waiver of documentation of consent will be requested for the caregiver survey. The survey will assess caregiver strain and burden, caregiver depression symptoms and behavioral symptoms of dementia and quality of life for the PWD. To streamline identification of caregivers of PWD, study staff will provide nurse care managers with a list of identified PWD and we will review medical records of persons with dementia to identify their caregivers.. Study staff will request that nurse care managers verify the primary caregiver for each PWD. Caregivers of PWD will be sent an invitation letter by mail (caregivers). The invitation letter will be accompanied by a study Fact Sheet about the study and will inform caregivers of their right to refuse participation. The Fact Sheet will address the following points: the research involves no more than minimal risk to the subjects; the waiver or alteration will not adversely affect the rights and welfare of the subjects; the research could not practicably be carried out without the waiver or alteration; and whenever appropriate, the subjects will be provided

with additional pertinent information after participation. If eligible participants refuse, there will be no further contact. If there is no response, we will call to confirm receipt of the letter, re-sending and/or and reviewing content as needed. If participant agrees to be interviewed, the interview will be scheduled. At the time of the interview, the interviewer will again repeat study fact sheet details and proceed if the respondent consents.

- The survey of Caregivers will be administered by phone in both English and Spanish to ensure responses from diverse patient and caregiver populations. Spanish versions will be administered by an experienced native Spanish language health care surveyor with over four years of experience. Care-giver respondents will be offered a \$25 bank gift card, via Forte, in appreciation of their time and effort. Based on our prior experience, we expect 50% to 60% of PWD caregivers will respond. We will assess the extent to which patients with less severe dementia would be able to self-report their symptoms, but for this pilot only caregivers will be surveyed.

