4 STUDY POPULATION AND INCLUSION CRITERIA

The study population consists of all PWD who actively received care management services from the 30 selected nurse care managers at the time of early training.

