6 SAMPLE SIZE

Preliminary estimates based on 2018 data suggested that on average FTE iCMP nurse care managers in our health system have 10 Medicare beneficiaries diagnosed with dementia on their panels. For this pragmatic quality improvement trial, we planned to engage 30 active iCMP nurse care managers (out of a total of approximately 65 nurse care managers) serving approximately 300 PWD and their caregivers (150 in each arm).

Among the 30 nurse care managers actually selected for the study, a total of 393 PWD met the inclusion criteria, 206 patients corresponding to the 15 intervention nurses and 187 patients corresponding to the 15 control nurses. The population was refined to exclude patients without a designated caregiver, deceased or moved to skilled nursing facility (for full list of exclusions see Figure 1 of cohort flowchart). This validated cohort included 143 PWD in the intervention group, and 113 PWD Controls.

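### The patient cohort is dated to early training, after nurses can know their arm, and the same nurses verify the caregivers on whom entry to the ED analysis depends

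*Protocol*

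**What the plan says.** **Cohort date.** Protocol 4 includes PWD who are "actively receiving care management services from a selected nurse care manager at the time of early training (end of month 3"). Protocol 3 limits patient-level measurement to those "actively engaged with care management as of the date care managers in the early training cohort are trained". SAP 4 uses PWD who "actively received care management services from the 30 selected nurse care managers at the time of early training". The Précis (Sample Size and Population) agrees.

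**Notification.** In Protocol 4.3 the 30 nurses are identified and randomised, and an e-mail "will be sent to the selected nurses informing them of their training date". Protocol 5.1 adds: "Prior to the 1-day in-person training, the care managers will engage in approximately 60 minutes of e-learning". Masking covers PWD and caregivers (Protocol 5.2) and survey interviewers (Protocol 10.1). It does not cover nurses.

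**Nurse input on caregivers.** Under Protocol 6, staff give each nurse a list of PWD and review records. Then: "Study staff will request that nurse care managers verify the primary caregiver for each PWD". Protocol 4.1 allows a caregiver to be named by the care manager, the health record or the PCP. Protocol 4.3 and 6.2.2 expect that the structured Epic fields will not be enough. No deadline for verification is set relative to the e-mail.

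**Caregiver as a condition of entry.** Protocol 4.1 and 4.2 set no caregiver condition for PWD. SAP 6 does: from 206 and 187 PWD meeting the inclusion criteria it removes those with no designated caregiver, together with deaths and moves to skilled nursing. "This validated cohort included 143 PWD in the intervention group, and 113 PWD Controls". SAP 7.1.1 draws the ED cohort (126 and 105) from that set.

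**Active status.** Protocol 6 lists patient status among the measures that iCMP collects. It does not say who sets it, and Protocol 4.1 does not define active engagement.

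**The concern.** Randomising nurses protects a comparison of their patients only if the set of patients cannot depend on the nurse's arm. Here the set is settled after the nurse can know the arm, and one step that decides membership of the ED cohort uses that nurse's input. If early and delayed nurses confirmed caregivers at different rates or for different kinds of patient, the ED cohorts would differ in caregiver support for reasons unrelated to any training effect. Caregiver support plausibly bears on both ED use and caregiver distress.

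SAP 8.1 adjusts for baseline utilization, race, ethnicity and age. It names no measure of engagement or caregiver support, so adjustment would not reliably remove such a difference. It matters even in a pilot: SAP 2.2 and 8.1 make the between-arm comparison of change in ED visits the primary outcome analysis, and Protocol 9.2 intends the data to support effect sizes for a full-scale study.

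**Working it through.** **1. Order of events.** There are two arms with different training dates, so being told the date discloses the arm. Notice of a training date must come before the training. The cohort date is the early training itself. It follows that the cohort is fixed after nurses can know their arm. The documents give no calendar date for the e-mail, the PWD list or the verification, so whether verification in fact came before or after notification is unknown.

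**2. The plan's own counts.** Planned: 30 nurses x 10 PWD = 300, or 15 x 10 = 150 per arm, as stated. SAP 6: 206 + 187 = 393, as stated, or 393/30 = 13.1 PWD per nurse.

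**3. Retention by arm (SAP 6 and 7.1.1).**

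| Step | Intervention | Control | Difference (points) |
|---|---|---|---|
| Eligible to validated | 143/206 = 69.4% | 113/187 = 60.4% | 9.0 |
| Validated to ED cohort | 126/143 = 88.1% | 105/113 = 92.9% | -4.8 |
| Eligible to ED cohort | 126/206 = 61.2% | 105/187 = 56.1% | 5.0 |

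Removed at validation: 206 - 143 = 63 (30.6%) and 187 - 113 = 74 (39.6%). At the intervention rate, 187 x 143/206 = 129.8 controls would have stayed, about 17 more than 113.

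**4. Uncertainty in the 9.0-point gap, ignoring clustering.** Unpooled SE = sqrt(0.694 x 0.306/206 + 0.604 x 0.396/187) = 0.048, so the 95% CI is 9.0 ± 1.96 x 4.8, or -0.4 to 18.4 points. Pooled proportion 256/393 = 0.651; SE = sqrt(0.651 x 0.349 x (1/206 + 1/187)) = 0.048; z = 1.87, p = 0.062.

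**5. Allowing for clustering.** Design effect = 1 + (13.1 - 1) x ICC. The documents give no ICC, so the values below are assumptions.

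| ICC | Design effect | p |
|---|---|---|
| 0.01 | 1.12 | 0.078 |
| 0.05 | 1.6 | 0.14 |
| 0.10 | 2.21 | 0.21 |

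**6. Through to the ED cohort.** The 5.0-point difference has a 95% CI of -4.7 to 14.8 and p = 0.31, before clustering.

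**7. What cannot be computed.** SAP 6 pools the caregiver, death and nursing-facility exclusions, and the flowchart is not in the text available, so the caregiver-related share by arm is unknown.

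**8. A separate sequencing conflict.** Protocol 6 sends the baseline survey to caregivers of the eligible cohort in month three, before launch. Protocol 4 dates eligibility to training at the end of month 3. Protocol 5.1 says: "Nurses in the early training cohort will receive their training in month three or month four". A PWD who becomes active after the survey list is drawn is eligible without a baseline; one who leaves iCMP in between is surveyed and then ineligible. This applies to both arms alike.

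**The case against.** Much of cohort entry is outside the nurse's reach. The diagnosis comes from a fixed claims window, ACO alignment from Medicare, and the PWD list from study staff. Caregivers can also be found through records or the PCP. No passage says that early nurses would name caregivers more readily, and delayed nurses are to be trained too. If the ED analysis kept PWD regardless of caregiver, the caregiver route would close.

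The counts give little support for selection. Entry of 206 v 187 against an even split gives z = (206 - 196.5)/sqrt(393 x 0.25) = 0.96, p = 0.34, ignoring clustering. The baseline differences in SAP 7.2 are weak evidence as well. That section flags standardised differences of 0.15 or more; with 126 and 105 PWD the SE is about sqrt(1/126 + 1/105) = 0.13, so chance alone passes 0.15 about 26% of the time per variable, before clustering. Baseline ED use was examined and is not listed as different. The primary objective is feasibility, and SAP 8.1 states no directional ED hypothesis.

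These points stand, and they limit the finding to a route by which entry could differ. They do not close the route. The claims window and the staff list do not govern caregiver designation, and similar net retention does not show similar composition.

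A reader might also infer that nurses control active status. Protocol 6 does not say so; in a nurse-led program it is a plausible inference and no more. Nor does Protocol 4 make PWD entry depend on a caregiver: that dependence arises in SAP 6.

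**Conclusion.** The weakness is in the design as written. The cohort is dated after nurses can know their arm, verification by those nurses is not required to come before notification, and SAP 6 makes a designated caregiver a condition of reaching the ED analysis. Entry to the primary analysis could therefore differ by arm. This rests on two readings: that the training-date e-mail discloses the arm, and that nurse verification can affect whether a PWD counts as having a designated caregiver.

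It would be wrong to read the 9.0-point validation gap, or the baseline differences, as showing that selection occurred. The interval includes zero, p is 0.08 to 0.21 across the assumed ICCs, the gap narrows to 5.0 points by the ED cohort, and the exclusion reasons are pooled. The data are compatible with chance. The survey-timing conflict is a matter of reconciling passages, not evidence of a difference between arms. The case for change is that it is cheap and closes a recognised route to post-randomisation selection in a cluster design.

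**What to change.** **In the plan.** In Protocol 3, 4 and 4.3 and SAP 4, define the cohort as a roster snapshot from iCMP status and Medicare claims, dated before the training-date e-mail. Define active engagement and state who records it. Require caregiver verification to be complete before that e-mail. Use the same roster for the baseline survey, and reconcile the training-month and survey-timing statements in Protocol 4, 5.1 and 6.

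**For data already collected.** The SAP is written after enrolment, so the sequence cannot be changed for this cohort. Where historical status can be retrieved from the warehouse, rebuild the roster as of the day before notification and add a sensitivity ED analysis on it by randomised nurse. Report each exclusion by reason and arm, with its timing relative to notification. If the flowchart already gives reasons by arm, only the timing needs adding.

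**Cost.** Prospectively, this is one changed date and a resequenced e-mail. PWD who join a panel between notification and training are left out. The retrospective step depends on archived status being available, which the documents do not confirm.
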